 - Patients with ≤PR at completion of 4 cycles, will stop therapy and be taken off protocol at completion of 4 cycles.

- For patients achieving >PR at end of 4 cycles, patients will continue to receive combination therapy with maximum up to 12 cycles.
 - Patients obtaining CR/sCR at any point during cycles in serum and urine will undergo MRD testing using multi-parametric flow cytometry.
 - Patients who attain minimal residual disease (MRD) negative status will stop treatment after 2 additional cycles (maximum 12 cycles).
 - Patients who are MRD positive will stop treatment at completion of 12 cycles. Patients converting from MRD positive status to negative status on subsequent MRD testing can stop after 2 additional cycles
 - Patients achieving <CR/sCR (and >PR at end of 4 cycles) will stop treatment at completion of 12 cycles.
- Upon completion of protocol therapy, patients will be encouraged to proceed onto maintenance therapy or high dose therapy with stem cell rescue under a separate treatment protocol or standard of care. If clinically indicated, patients may need alternative therapy.
- After completion of protocol therapy, patients will remain on study for an additional 3 years for survival analysis.

[figure not shown]
Treatment Plan (see schema below)

- Cycle 1 ONLY: Carfilzomib 20 mg/m² per dose, days 1 and 2; Carfilzomib 45 or 56 mg/m² per dose, days 8, 9, 15, and 16
- Cycles 2- up to 12: Carfilzomib 45 or 56 mg/m² per dose, days 1, 2, 8, 9, 15, and 16
- Cycles 1- up to 12: Lenalidomide 25 mg/day, days 1–21 every 28 days
- Cycles 1-4: Dexamethasone 20 mg/dose, days 1, 2, 8, 9, 15, 16, 22, and 23
- Cycles 5- up to 12: Dexamethasone 10 mg/dose, days 1, 2, 8, 9, 15, 16, 22 and 23
- After receiving first 4 cycles, patients who are considered to be eligible for subsequent high dose therapy/autologous stem cell transplant (ASCT) will undergo autologous stem cell harvesting for potential use in the future. For patients who choose to undergo stem cell harvest, next cycle may be delayed for up to 7 weeks.
- If patients achieve > PR after completion 4 cycles, patients may receive additional combination therapy (maximum permissible 12 cycles). Patients may go onto receiving additional maintenance phase therapy with lenalidomide under a separate treatment protocol.
 - Patients obtaining CR/sCR and MRD negative status by flow cytometry will stop treatment after 2 additional cycles (maximum 12 cycles) delivered.

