 - Patients obtaining CR/sCR and MRD positive status by flow cytometry will stop treatment after completing 12 cycles. Patients converting from MRD positive status to negative status on subsequent MRD testing can stop

after 2 additional cycles

- Patients achieving <CR/sCR will stop treatment after completing 12 cycles.
- Patients ≤PR after completing 4 cycles will go off study therapy.
- Upon completion of protocol therapy, patients will be encouraged to proceed onto maintenance therapy or high dose therapy with stem cell rescue under a separate treatment protocol or standard of care. If clinically indicated, patients may need alternative therapy
- After completion of protocol therapy, patients will remain on study for an additional 3 years for survival analysis.

Schema

* After 4 or more cycles, patients considered transplant eligible will be recommended for stem cell collection. Stem cell collection is not part of the current protocol.

**For patients with non-evaluable samples at MRD assessments byflow cytometry, patients can opt for a repeat assessment or continue with up to 12 cycles of CRd therapy.

***Patients converting from MRD positive status to negative status on subsequent MRD testing can stop after 2 additional cycles

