At the National Cancer Institute, we recently published results of a phase II clinical and correlative study of CRd in patients with newly diagnosed MM patients¹{Korde, 2015 #4573}. Patients were administered eight 28-day cycles of therapy including carfilzomib IV 20/36 mg/m² (based on prior Jakubowiak trial) on days 1, 2, 8, 9, 15, 16. After 8 cycles of CRd, all patients with stable disease (SD) or better receive cycles 9–20 of lenalidomide

maintenance 10 mg days 1–21. Of the 45 patients evaluable for toxicity and response, none reported \geq grade 3 neuropathy. This finding stands in sharp contrast with bortezomib, which can be associated with sensory neuropathy in up to 80% of treated patients when used in combination with lenalidomide and dexamethasone¹³. The CRd regimen (using 36 mg/ m²) resulted in rapid and deep responses with an overall response rate of 98% (n=42) and sCR/CR in 56% (n=25). The median time to sCR was 5 cycles (range 2-18).

Minimal Residual Disease Testing in Myeloma

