- m. After 1- and 3-year from completing therapy, PFS and OS data will be collected on patients. Patients will option of having formal evaluation with H&P, clinical labs, myeloma labs and bone marrow evaluating for MRD status. PFS and OS data may be collected over the phone along with review of medical records. Survival, PFS, and time to next line of treatment data may be collected on subsequent protocols that patients have consented for (maintenance protocols/bio-banking or storage protocols).
- n. Patients will have an EKG and echocardiogram (2-D or strain) performed at baseline and after completion of 4 cycles of therapy. Outside echocardiograms are permissible

Clinical and Correlative Studies - To create a bone marrow (clinical pathology, whole BM lysate, CD 138+ fractions and CD 138- fractions cell sorting with subsequent correlatives on both fractions), peripheral blood, and urine sample bank. These samples may be used to later to evaluate biological activity of carfilzomib, lenalidomide, and dexamethasone. Timepoints and potential analyses are listed below:

Bone Marrow

Sampling Time Points of Bone Marrow correlative studies

- a) Baseline
- b) CR/sCR during cycles 2-and up to 12
- c) End of therapy
- d) 1 and 3 year timepoints after completing therapy (optional)

| | Baseline | During Cycles 2-12 if reaches CR/sCR | End of study therapy | 1 and 3 year timepoints after completing therapy |
|---|-----------------|---|---------------------------------|---|
| Pathology/IHC | x | x | x | x |
| Multiparametric Flow Cytometry | x | x* | x* | x |
| FISH/Cytogenetics | x | | | |
| Molecular Pathology for light or heavy chain immunoglobulin rearrangement | x | x | x | x |
| Storage (sorted and whole cell lysate) | x | x | x | x |

*Patients undergoing MRD evaluation or End of study evaluation, the first pulled sample will be sent for Multiparametric flow cytometry. For those patients that are MRD negative by flow cytometry during their routine pre-stem cell collection bone marrow assessments, the result will count towards their MRD evaluation.

- Potential studies on the stored bone marrow samples may include but are not limited to the following:

Bone Marrow Aspirate/Biopsy

Pathology/Immunohistochemistry

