Immunohistochemical staining will be assessed using immunohistochemistry markers such as CD 138, light chains, CD56 etc. Microenvironment interactions will also be assessed using various immunohistochemistry markers for osteoblasts, osteoclasts, stromal cells and proteasome components.

Minimal Residual Disease

Flow cytometry: Immunophenotyping of aberrant plasma cells by flow cytometry currently involves, but is not limited to, the use of the following reagents: CD138, CD19, CD45, CD38, and CD56. Characteristic changes in immunophenotypically abnormal plasma cells (CD38 bright and/or CD138 positive) include but are not limited to decreased or absent CD19 and CD45, decreased CD38, increased CD56, decreased CD27, decreased CD81, increased CD117. For patients with non-evaluable samples at MRD assessment, patients can opt for repeat MRD assessment or continue to receive a total of 8 cycles of CRd. For those patients that are MRD negative by flow cytometry during their routine pre-stem cell collection bone marrow assessments, the result will count towards their MRD evaluation. The first pulled bone marrow sample will be sent for multi-parametric flow cytometry as a priority. Samples will undergo MRD testing per MSK institutional practice, see section 12.0 for further methodology practice.

Molecular pathology: For MRD samples utilizing the NGS LymphoSIGHT™ (Sequenta, Inc., South San Francisco, CA) platform, immunoglobulin heavy and kappa chain variable, diversity, and joining gene segments from genomic DNA obtained from CD138+ bone marrow (BM) cell lysate or cell-free supernatant BM aspirate were amplified using universal primer sets as described elsewhere²¹. An MM clonotype was defined as an immunoglobulin rearrangement identified by NGS at a frequency of $\geq 5\%$.

Mass spectrometry based proteomics for minimal residual disease assessment: Serial urine and serum samples will be analyzed to detect clonotypic peptides representing patient's monoclonal immunoglobulin heavy and light chains using high resolution mass-spectrometry-based proteomics.

FISH and cytogenetics

Interphase FISH/cytogenetics will be performed on patients enrolled in this protocol.

DNA-based target mutations

Bone marrow aspirate samples will be analyzed for somatic mutations by exome-sequencing of targeted genes using FoundationOne Heme platform (or equivalent i.e. MSK Impact Heme). After therapy, perform if response is ≤PR or evidence of gross residual disease on SPEP/UPEP

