For patients undergoing MRD or end of study assessment, the first pulled bone marrow sample will be sent for multi-parametric flow cytometry as a priority. Flow cytometry based assay to rule out MRD (defined as less than 20 abnormal plasma cells) in bone marrow aspirates of CR/sCR patients. For patients with samples demonstrating between 10-20 abnormal plasma cells, cases will be reviewed with hematopathologist and clinical investigator on a case by case basis to determine whether sample is considered MRD positive. Patients with <CR/sCR are considered MRD positive. We will use the MSKCC flow cytometry MRD method which is based on 10-colors in a single tube.¹⁶ The test demonstrates highly similar results when compared to the current Euroflow approach. This test is validated and already in clinical use at MSK. Immunophenotyping of aberrant plasma cells by flow cytometry currently involves, but is not limited to, the use of the following reagents: CD138, CD19, CD45, CD38, and CD56. Characteristic changes in immunophenotypically abnormal plasma cells (CD38 bright and/or CD138 positive) include but are not limited to decreased or absent CD19 and CD45, decreased CD38, increased CD56, decreased CD27, decreased CD81, increased CD117. For patients with non-evaluable samples at MRD assessment, patients can opt for repeat MRD assessment or continue to receive a total of 12 cycles of CRd. For those patients that are MRD negative by flow cytometry during their routine pre-stem cell collection bone marrow assessments,

the result will count towards their MRD evaluation.

Traditional Response Criteria from International Myeloma Working Group Criteria for Multiple Myeloma²²

Evaluation of Response Criteria

- a) Stringent Complete Response (sCR)
 - o Complete Response as defined below plus: Normal FLC ratio and absence of clonal cells in bone marrow by immunohistochemistry or immunofluorescence (presence/absence of clonal cells is based on the kappa/ lambda ratio).
- b) Complete Response (CR)
 - o Negative immunofixation on the serum and urine and disappearance of any soft tissue plasmacytomas and <= 5% plasma cells in bone marrow
- c) Very Good Partial Response (VGPR)

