The phase II component of this trial will explore the efficacy of the combination therapy using the carfilzomib dose selected in the phase I trial. The primary endpoint is CR/sCR MRD negativity (MRD-) rate by flow cytometry upon or prior to completion of 12 cycles of therapy. Patients with <CR/sCR are considered MRD positive. Based on previous research an CR/sCR MRD- rate by flow cytometry of 45% would be promising enough to warrant further investigation, while a rate of 20% would not be promising for further investigation. Using a Simon's optimal two-stage design, the first stage of the trial will enroll 14 patients. This includes the three-six patients treated at the MTD in the phase I trial. If three patients or fewer are CR/sCR MRD- by flow cytometry, the trial will stop due to a lack of efficacy; otherwise, an additional 11 will enroll to a total sample size of 25 at end of phase II. If at least eight patients are MRD- (at the MTD), the intervention will be considered promising for further research. The type I error is set at 0.10 and the type II error is set at 0.10. If the true MRD-rate is 20%, the probability of early termination is 70%. For patients that come off trial prior to completion of 4 cycles of therapy, due to reasons unrelated to disease progression or toxicities, patients can be replaced (max 3) for MRD evaluation as part of the phase II assessment.

It is anticipated that 1-2 patients per month may enroll on this trial; thus, approximately one year is anticipated as the accrual period for the phase II study. The total maximum possible projected sample size for the study is 37 patients.

Secondary endpoints for both Phase I and II:

1. To estimate the overall response rate (ORR) according to International Myeloma Working Group criteria at each cycle and as the best response during the treatment of up to 12 cycles. In addition to ORR, the rates of VGPR+CR and CR alone will also be estimated and reported. The exact 95% confidence intervals will also be included.
2. Kaplan-Meier methodology will be used to estimate progression-free survival and overall survival. Estimates of survival along be with 95% confidence intervals will be provided for select time points.

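### Section 10 stops a patient with a non-evaluable, unrepeated MRD sample at 8 cycles; Section 12 gives the same rule with 12, and 12 is the figure that fits the rest of the plan

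*Combined protocol and SAP*

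**What the plan says.** Two places give an instruction for a patient whose MRD flow sample is non-evaluable, and the schema gives a third.

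- Section 10.0, Minimal Residual Disease, flow cytometry paragraph: "patients can opt for repeat MRD assessment or continue to receive a total of 8 cycles of CRd".
- Section 12.0, Minimal Residual Disease: "patients can opt for repeat MRD assessment or continue to receive a total of 12 cycles of CRd".
- Section 1.0, second footnote to the schema: "patients can opt for a repeat assessment or continue with up to 12 cycles of CRd therapy".

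The surrounding treatment and assessment rules all use 12.

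- The list of marrow time points in Section 10.0 includes "CR/sCR during cycles 2-and up to 12", and the table below it has flow cytometry in the cycles 2 to 12 column.
- Section 1.0, repeated in Section 4.2: "Patients who are MRD positive will stop treatment at completion of 12 cycles". Patients who continue past cycle 4 with less than CR/sCR also stop at 12. Patients found MRD negative receive two further cycles, capped at 12 in total.
- Section 14.0 counts MRD negativity for the primary endpoint "upon or prior to completion of 12 cycles of therapy".

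The flow cytometry paragraph of Section 10.0 refers the reader to Section 12.0 for assay methodology. It does not say that Section 12.0 overrides its cycle count.

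**The concern.** This is a rule about how long to treat. Two clinicians who each follow the protocol could give the same patient 8 or 12 cycles, and either choice departs from one section.

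Treatment duration is part of the regimen under test, and the trial adapts it to MRD status. Under the Section 10.0 figure, a patient whose status is unknown could be treated for less time than one known to be negative, and always for less than one who stays positive. That runs against the response-adapted logic of Sections 3.2 and 4.2. Stopping at 8 also brings forward the end-of-therapy marrow and removes cycles 9 to 12 as a period in which the patient might become MRD negative.

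**Working it through.** **1. Do the instructions conflict?** The triggering event (a non-evaluable sample) and the first option (repeat the test) are the same in Sections 10.0 and 12.0. Only the total differs, 8 against 12. A total is a fixed number, so this is a direct contradiction. The schema footnote sets a ceiling of 12, and 8 lies below it. The footnote therefore supports 12 but does not by itself contradict 8.

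**2. Which figure fits the plan?** Let k be the number of completed cycles at the MRD test. Sections 1.0 and 4.2 give these total cycles:

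- MRD negative: min(k + 2, 12)
- MRD positive and remaining so: 12
- Non-evaluable and not repeated: 8 under Section 10.0, 12 under Section 12.0

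| k | Negative | Positive | Unknown, Section 10.0 | Unknown, Section 12.0 |
|---|---|---|---|---|
| 6 | 8 | 12 | 8 | 12 |
| 7 | 9 | 12 | 8 | 12 |
| 8 | 10 | 12 | 8 | 12 |
| 9 | 11 | 12 | 8, already exceeded | 12 |

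At k = 6 the unknown patient is treated like a confirmed negative. At k = 7 and 8 the unknown patient stops before a confirmed negative would. From k = 9 the Section 10.0 rule cannot be carried out, although the same section schedules samples up to cycle 12. With 12 in its place, none of these anomalies occurs. The 12-cycle endpoint window in Section 14.0 agrees with 12. It is supporting evidence only, since a result obtained at 8 cycles also falls inside it.

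**3. Size for one affected patient.** The loss is at most 12 − 8 = 4 cycles, when the sample is taken by the end of cycle 8. With 28-day cycles, 4 × 28 = 112 days. As a share of the maximum, 4/12 = 33%.

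**4. Does it reach the statistical design?** Section 14.0 stops at 3 or fewer MRD-negative patients of 14 and declares the regimen promising at 8 or more of 25. With b(x; n, p) the binomial probability:

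- Early stopping at p = 0.20: Σ b(x; 14, 0.20) for x = 0 to 3 = 0.698. The plan states 70%.
- Probability of declaring promising: Σ b(x; 14, p) × P(Bin(11, p) ≥ 8 − x) for x = 4 to 14. At p = 0.20 this is 0.093 (type I error, limit 0.10). At p = 0.45 it is 0.903 (type II error 0.097, limit 0.10).

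The plan's figures are reproduced. No term contains the cycle count, so choosing 8 or 12 leaves these figures as they are.

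**The case against.** The strongest case is that this is a one-digit slip with little reach. The 8 stands among assay descriptions for the marrow samples, not in the treatment plan. Every treatment section runs to 12, the schema addresses non-evaluable samples directly, and the trial is run at one centre. The rule applies only if a sample is non-evaluable and the patient does not repeat it. Even then, footnote h to the Section 10.0 schedule makes the end-of-therapy marrow mandatory unless negativity was confirmed earlier, so the patient can still be counted as MRD negative.

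All of this stands, and it limits the weight of the point. It does not remove the contradiction, because the sentence in Section 10.0 is an instruction on treatment length and nothing tells the reader to disregard it.

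A second argument is that 8 might be deliberate. The earlier study described in Section 3.1 gave eight cycles, so the figure may have been carried over. The documents do not say so, and no passage offers a reason for 8 in this trial.

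A reader might also infer that the conflict biases the primary endpoint or undermines the two-stage design. The documents do not support that. They give no expected non-evaluable rate for this trial. The earlier study reports flow results for all 25 of its CR/sCR patients, but this trial uses a different platform (the centre's own 10-color assay), and Section 3.1 itself stresses how much flow methods vary between institutions. The rule is also not confined to the 25 phase II patients, since the study may enrol up to 37. A patient count built on those inputs would not be reliable.

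**Conclusion.** The inconsistency is real and Section 10.0 is wrong as written. The direct conflict is between Sections 10.0 and 12.0, with the schema as support for 12. For one affected patient the cost is up to 4 cycles (112 days) of therapy and a shorter period in which MRD negativity can be found. It is not the loss of the endpoint assessment.

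The expected impact on the trial is minor. The number of patients affected is likely small, because two conditions must both hold (a non-evaluable sample and no repeat), but the documents do not allow an estimate. The conclusion that 12 is the intended figure assumes that the 12-cycle rules elsewhere reflect current intent, and every related passage points that way. The point is worth correcting because it governs treatment length, not because it threatens the analysis.

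**What to change.** In the flow cytometry paragraph under Minimal Residual Disease in Section 10.0, change the total for a non-evaluable, unrepeated sample from 8 cycles to 12, so that it matches Section 12.0. Nothing else needs to change for this point. The cost is a clarifying text amendment, with no added patients or procedures and no change to the endpoint, sample size or stopping rule.

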11.0 TOXICITIES/SIDE EFFECTS

11.1 Carfilzomib

Likely Side Effects: those occurring in more than 20% or more than 20 out of 100 persons who receive carfilzomib:

- Fatigue (tiredness)
- Fever
- Headache
- Cough

- Shortness of breath (at rest or with exertion) which in rare cases may be life-threatening or resulting in death
- Nausea
- Vomiting
- Diarrhea
- Constipation
- Decreased red blood cell count which may lead to feeling tired
- Decreased platelet counts which may lead to increase bleeding or bruising
- Decreased white blood cell count which may decrease your ability to fight infection
- Upper respiratory tract infection
- Mild decreases in kidney function which are generally reversible
- Swelling of the arms or legs
- Back pain
- Inflammation of the liver (mild, reversible changes in liver function tests)

Less Likely Side Effects: those occurring in 5-20% or 5 to 20 out of 100 persons who receive carfilzomib:

- Flu-like symptoms such as fever, chills, or shaking that may occur at any time but are more likely to occur on the day of or the day after carfilzomib infusion
- Decreased or worsening of heart function including chest pain, abnormal heart rhythm, heart attack, and heart failure. This can be serious, potentially life threatening event.
- Loss of or decreased appetite which may lead to weight loss
- Insomnia (difficulty sleeping)
- Dizziness
- High blood pressure
- Abnormal physical weakness or lack of energy
- Blurred or double vision
- Numbness, tingling, painful or decreased sensation in hands and/or feet
- Blood chemistry and electrolyte alterations
- Rash and/or itching, or dry skin
- Pneumonia
- Pain, burning, or irritation at the infusion site
- Generalized pain
- Pain in the bones or joint pain or extremities
- Muscle spasm, pain, or weakness

Rare and/or Potentially Serious Side Effects: these have occurred in less than 5% or in less than 5 out of 100 persons who receive carfilzomib:

- Herpes zoster reactivation
- Liver failure
- Acute kidney failure
- Increase in the blood pressure in the arteries of the lungs (Pulmonary Hypertension)
- Infusion reactions (which can occur during or shortly after carfilzomib infusion) including flushing or feeling hot, fever, shakes, nausea, vomiting, weakness, shortness of breath, swelling of the face, pain in the muscles or joints, tightness or pain in the chest, and low blood pressure
- Allergic reaction including total blood rash, hives, and difficulty breathing
- Tumor Lysis Syndrome: Caused by rapid killing of tumor cells during dosing. When the tumor cells die, they release their contents into the bloodstream. If cell killing is very rapid, this can affect

blood chemistries and the kidneys. In severe cases, this can lead to shutdown of kidney function requiring dialysis

- Posterior reversible encephalopathy syndrome (PRES): A rare condition that causes swelling of the brain and affects how it functions. A person with PRES may experience headaches, confusion, loss or decreased level of consciousness, blurred vision or blindness, seizures, and possibly death. If caught early and treated, PRES may be reversed.

